4.1.3 Safety Review Committee (SRC)

An SRC comprised of the Medical Monitor, enrolling PIs, and Sponsor representatives will hold periodic teleconferences to evaluate the safety and treatment status of all subjects available during the Safety Run-in (Part 1) at several stages:

- after 6 subjects Arm A have completed the first cycle,
- after 3 subjects in Arm C have completed the first cycle,
- at any other time as needed following random assignment in Part 2.

The safety run-in of Arm C (n=3) will occur with a 1-week interval between dosing of subjects and an SRC will convene after all subjects have received 1 cycle of therapy. The SRC has the authority to recommend dose or regimen modifications for safety concerns.

A written summary documenting the results and recommendations of each review will be provided to the investigator(s) and maintained on file with the Sponsor. Additional sub-investigators and personnel may participate in reviews, as appropriate.

Following a treatment arm review, the SRC may recommend proceeding with enrolling additional subjects in the current treatment arm or not enrolling any additional subjects.

While the SRC is expected to reach a consensus opinion regarding any premature discontinuation or significant modification of the study, the Sponsor may independently stop the study at any time.

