5.3 Withdrawal of Subjects from Study Treatment and/or Study

The investigator and/or the subject have the right to terminate the subject's participation in the study at any time. Subjects who discontinue study drug should complete the Post-Treatment Safety Assessment visit.

A subject **may** withdraw (or be withdrawn) from the study treatment prematurely for any of the following reasons:

- PI determines further participation is not in subject's best interest.
- Clinically significant disease progression

NOTE: In the absence of rapid clinical deterioration, disease progression should be confirmed by a repeat, consecutive assessment no less than 4 weeks from the date first documented to ensure that more slowly declining total tumor burden in response to therapy is not missed.

A subject **MUST** be withdrawn in the event of any of the following:

- Withdrawal of informed consent.
Note: Any subject who wishes to withdraw from the study treatment may do so but will be counseled that follow-up for the effects of immunotherapy is strongly recommended.
- Any treatment-related AE meeting withdrawal criteria.
- Substantial noncompliance with the requirements of the study.
- Subjects with a confirmed positive pregnancy test.
- Any intercurrent illness that would, in the judgement of the investigator, affect assessments of clinical status to a significant degree and require discontinuation of protocol therapy.

Every effort should be made to follow subjects who withdraw from study treatment with ongoing treatment-related AEs in order to determine the outcome of the event.

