5.4 Replacement of Subjects

Should a subject discontinue study treatment before receiving 6 cycles for reasons other than progression, another subject may be added to that study arm for full analysis.

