6.2.5 Retreatment Criteria, Dose Delays and Modifications

Subjects may receive up to 6 cycles of study drug treatment. To receive each repeat treatment cycle, all treatment-related AEs must have resolved to Grade 1 or baseline and the following laboratory criteria must be met:

Hemoglobin \geq 9 g/L	eGFR \geq 60 mL/min/1.73 m ²
Lymphocytes $>$ 700/ mm ³	AST and ALT \leq 2.5 x ULN For subjects with documented liver metastases, ALT and AST \leq 5 \times ULN
Neutrophils \geq 1,500/ mm ³	Total bilirubin $<$ 1.5 x ULN
Platelets \geq 100,000/ mm ³	INR and PTT $<$ 1.5 x ULN

Clinical laboratory tests drawn pre-treatment for analysis on Day 1 of each cycle may be used for determining if the re-treatment criteria have been met, and must be reviewed by the investigator or designee prior to the next cycle of study drug administration. Two treatment delays for recovery to acceptable levels are allowed at weekly intervals up to a maximum of 14 days. In the event that a treatment-related dose delay is necessary for palifosfamide, then the next cycle of study treatment will be administered at 80% of the dose ([Table 3](#)). If an AE is clearly related to 1 study drug and not the other (in combination Treatment Arm C), then dose modification/delay is to occur for the relevant study drug (INXN-1001 and/or palifosfamide). A maximum of two dose reductions, of either INXN-1001 or palifosfamide, will be allowed.

Table 3. Dose Modifications for Palifosfamide-related Toxicity^a

ADVERSE EVENT	PALIFOSFAMIDE
Hematologic	
Platelet count <100 × 10 ⁹ /L	Delay dose of palifosfamide up to 14 days until platelet count ≥ 100 × 10 ⁹ /L, then reduce by 20%.
ANC < 1500/mm ³	Delay dose of palifosfamide up to 14 days until ANC returns to ≥ 1500, then maintain dose when restarted.
Neutropenic fever	Delay dose of palifosfamide up to 14 days until resolved, then reduce by 20%.
Any Grade 4 hematologic toxicity	Delay dose of palifosfamide up to 14 days until Grade ≤ 1 or baseline, then reduce by 20%.
Estimated Glomerular Filtration Rate (eGFR) (Appendix 5)	
≥25% up to <50% decrease from baseline ^b	Hold dose until repeat test is performed. Reduce dose of palifosfamide by 20% if confirmed on repeat test.
≥50% decrease from baseline ²	Hold dose until repeat test is performed. Discontinue palifosfamide if confirmed on repeat test.
Non-hematologic (other than creatinine or urinary electrolyte wasting)	

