Not treatment-related Grade 3 if unresponsive to appropriate therapy.	Delay dose of palifosfamide for up to 14 days until Grade ≤ 1 or baseline, then reduce by 20%.
Not treatment-related Grade 4	Delay dose of palifosfamide up to 14 days until ≤ Grade 1 or baseline, then reduce by 20%.

^aWhen indicated, the maximum permitted delay of study drug administration due to toxicity and/or for confirmatory laboratory testing is 14 days.

^bBaseline eGFR determined based on the most recent serum creatinine measurement prior to study drug administration (ie, Cycle 1 Day 1 or Screening).

Subjects who experience a treatment-related Grade 4 AE, other than nausea and/or vomiting in the absence of optimal treatment with antiemetics, will be discontinued from study treatment. If, however, the subject has experienced a substantial benefit from treatment and the PI and Medical Monitor recommend continuation on the study, re-exposure to the experimental treatment may proceed on a case-by-case basis.

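### Section 6.2.5 gives two instructions for a treatment-related Grade 4 hematologic event in Arm C (resume palifosfamide, or stop study treatment) and does not say which prevails

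*Protocol*

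**What the plan says.** Table 3 in Protocol Section 6.2.5 sets palifosfamide dose changes for toxicity. Its last hematologic row is triggered by "Any Grade 4 hematologic toxicity", and the action is "Delay dose of palifosfamide up to 14 days until Grade ≤ 1 or baseline, then reduce by 20" percent. Three other hematologic rows also delay palifosfamide for up to 14 days:

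- platelets below 100 × 10⁹/L: wait for recovery to that level, then reduce by 20%;
- ANC below 1500/mm³: wait for recovery to that level, then restart at the same dose;
- neutropenic fever: wait for resolution, then reduce by 20%.

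None of these three rows stops applying above a given grade.

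The paragraph after the table says that subjects with a "treatment-related Grade 4 AE, other than nausea and/or vomiting in the absence of optimal treatment with antiemetics, will be discontinued from study treatment". The next sentence opens an exception if "the subject has experienced a substantial benefit from treatment and the PI and Medical Monitor recommend continuation on the study"; in that case "re-exposure to the experimental treatment may proceed on a case-by-case basis". Neither sentence refers to Table 3 or names a dose for re-exposure.

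**The concern.** A palifosfamide-related Grade 4 cytopenia meets the trigger of the table and the trigger of the paragraph. The table continues the subject; the paragraph stops the subject. With about 30 centers planned (Synopsis), one site could stop all study treatment and another could resume palifosfamide without involving the Medical Monitor, and each could point to Section 6.2.5.

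Three things depend on the answer:

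- **Subject safety.** Section 3.1 says the combination had not yet been studied in humans, and Section 6.2.4.4 asks for careful monitoring of hematologic toxicity with palifosfamide.
- **Consistency of the safety data.** Safety and tolerability is a primary objective, and Section 8.6.3 tabulates exposure and reasons for stopping treatment. The same event could be counted as a discontinuation at one site and a dose reduction at another.
- **Replacement.** Section 5.4 says: "Should a subject discontinue study treatment before receiving 6 cycles for reasons other than progression, another subject may be added to that study arm". A subject who is stopped for toxicity before Cycle 6 meets that condition. One who continues at a reduced dose does not.

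**Working it through.** No figure in the plan can be reproduced here. The check sets the two rules side by side and looks for anything that ranks them.

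**Step 1. Triggers and actions (Section 6.2.5).** The documents do not reproduce the CTCAE cut-offs. I assume that a Grade 4 neutrophil or platelet count lies below the threshold of the matching row.

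| Rule | Trigger | Limited by relatedness or grade? | Action |
|---|---|---|---|
| Platelet row | below 100 × 10⁹/L | No | Delay, then 20% lower |
| ANC row | below 1500/mm³ | No | Delay, then same dose |
| Neutropenic fever row | any | No | Delay, then 20% lower |
| Grade 4 hematologic row | any cause | Grade 4 only | Delay, then 20% lower |
| Paragraph after the table | Grade 4 AE | Treatment-related only | Stop study treatment, unless re-exposure is approved |

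Section 7.1 counts significant laboratory changes from baseline as adverse events, so a Grade 4 cytopenia falls under the paragraph.

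**Step 2. Apply the rules to cases.**

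- *Related Grade 4 neutropenia, no substantial benefit.* The ANC row restarts at 120 mg/m²/day, the Grade 4 row at 0.8 × 120 = 96 mg/m²/day, and the paragraph stops study treatment. These are three different outcomes.
- *Related Grade 4 neutropenic fever, no substantial benefit.* Two rows restart at 96 mg/m²/day; the paragraph stops.
- *Related Grade 4 event, re-exposure approved.* The paragraph permits treatment but gives no dose. The table can supply one, so there is no conflict over continuing.
- *Unrelated Grade 4 cytopenia.* The paragraph does not apply. For neutropenia, the ANC row and the Grade 4 row still give different doses.

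The conflict between table and paragraph is therefore confined to treatment-related Grade 4 events in subjects who do not qualify for re-exposure. That group is largest early on: the first scheduled tumor assessment is at week 12 (Cycle 5 Day 1). In Cycles 1 to 4, substantial benefit would have to rest on unscheduled imaging, photographs or clinical judgment.

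**Step 3. Look for a precedence rule.**

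- Section 6.2.5 directs modification or delay in Arm C to the drug responsible. It does not mention discontinuation.
- Section 6.2.6 deals with injection site reactions only.
- Section 7.2.2 links Grade 4 to stopping study drug, but only in its fallback scale for events that CTCAE does not define, and it does not refer to Table 3.
- Section 4.1.3 gives the SRC a general power: "The SRC has the authority to recommend dose or regimen modifications for safety concerns". It does not instruct a site at the time of the event.
- The SAP describes a single-arm, one-cycle study without palifosfamide and has no rule on this.

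Nothing ranks the two instructions.

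**Step 4. Illustrative size.** Assume an event in Cycle k (k = 1 to 5), recovery within 14 days, no second reduction, and all remaining cycles given.

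- Remaining cycles: 6 − k, that is 5 down to 1.
- At the reduced dose: 96 × 3 days = 288 mg/m² per cycle. For k = 1, 5 × 288 = 1440 mg/m²; for k = 5, 1 × 288 = 288 mg/m².
- Under the ANC row: 120 × 3 = 360 mg/m² per cycle, so 5 × 360 = 1800 down to 360 mg/m².
- INXN-2001 injections, if continued: 5 down to 1.
- Under the paragraph without re-exposure: 0 for each.
- An event in Cycle 6 leaves no further cycles under any rule.

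Arm C at most: 3 + 9 + 14 = 26 planned subjects.

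**The case against.** The best defense is a two-step reading: the paragraph decides whether treatment continues, and Table 3 decides how palifosfamide is resumed. On that reading the Grade 4 row still has a use, for unrelated cytopenias and for subjects approved for re-exposure. The reading is sensible, and the fix below adopts it, but the protocol does not state it. The row covers Grade 4 hematologic toxicity of any cause, in a table titled for palifosfamide-related toxicity, so a site may fairly apply it to a related event.

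A second defense is that the specific row governs over the general paragraph, helped by the Arm C sentence on the responsible drug. Against it, the paragraph names its one exempt event type and hematologic events are not in it. The non-hematologic Grade 4 row is expressly limited to events that are not treatment-related, which fits the paragraph; the hematologic row has no such limit. The two defenses also lead to opposite actions, so the text does not settle the matter.

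It is fair to add that the SRC may act at any time in Part 2, that replacement under Section 5.4 is optional, and that the number of affected subjects may be small or zero. These points limit the size of the problem but do not resolve it.

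**Conclusion.** Section 6.2.5 is wrong as written. This is an internal inconsistency in a safety rule, not a design choice. It concerns treatment-related Grade 4 hematologic events in Arm C subjects who do not qualify for re-exposure, and it reaches all four hematologic rows of Table 3. It should be fixed because it governs toxicity in a combination without prior human data and costs almost nothing to correct.

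Three stronger conclusions that a reader might draw are not supported:

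- *That continuing under Table 3 breaches the mandatory withdrawal rule.* Section 5.3 requires withdrawal for "Any treatment-related AE meeting withdrawal criteria" but does not list those criteria. Whether the Grade 4 paragraph is one of them is conjecture.
- *That the dose figures measure harm.* They are dose arithmetic under the assumptions in Step 4. The documents give no event rate, so the number of subjects affected cannot be estimated.
- *That the efficacy design is compromised.* No effect on power or type I error follows from this point.

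**What to change.** Add one precedence statement covering every row of Table 3, for example:

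*For a treatment-related Grade 4 event, the discontinuation rule below takes precedence over all rows of this table. If re-exposure is approved, resume palifosfamide after recovery to Grade 1 or lower or baseline within 14 days, reduced by 20%. For Grade 4 hematologic events that are not treatment-related, follow the Grade 4 row (reduce by 20%), not the ANC row.*

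If the sponsor instead wants Grade 4 cytopenias managed by dose reduction, it should do three things: exempt uncomplicated Grade 4 cytopenia by name in the paragraph, keep discontinuation for treatment-related Grade 4 neutropenic fever, and state that the Grade 4 row overrides the unchanged dose in the ANC row.

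Two shorter edits would not work. Rewriting only the Grade 4 row leaves the platelet, ANC and neutropenic fever rows in conflict with the paragraph. Exempting everything managed under Table 3 would remove the discontinuation default for Grade 4 neutropenic fever.

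The choice between the two rules is clinical and belongs to the sponsor. The cost is a short protocol clarification, with no change to sample size, visits or data collection.

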6.2.6 Severity Grading and Management of Injection Site Reactions

Injection of a biologic agent carries a potential risk of injection site reaction which is characterized as an intense reaction (usually immunologic) at or near the site of injection. Injection reactions will be graded according to the NCI CTCAE v4.03.

Table 4 outlines the injection site reaction grading system, associated symptoms, and the recommended actions to be taken. Reactions at the INXN-2001 injection site that occur within 24 hours after the injection and are attributed to INXN-2001 will be considered to be injection-related AEs.

Table 4. Injection Site Reaction Severity Grading and Management

CTCAE Grade	Symptoms	Course of Action
1	Tenderness with or without associated symptoms (e.g., warmth, erythema, itching)	No intervention required.
2	Pain; lipodystrophy; edema; phlebitis	Proceed with further dosing cycles.
3	Ulceration or necrosis; severe tissue damage; operative intervention indicated	Discontinue further study treatment and notify Medical Monitor. If toxicity meets seriousness criteria, immediately report as per SAE reporting procedures; see Section 8.4 .
4	Life-threatening consequences; urgent intervention indicated	Permanently discontinue study treatment and notify Medical Monitor. Defaults to “serious”. Immediately report as per SAE reporting procedures; see Section 8.4 .
5	Death	Immediately notify Medical Monitor and report as per SAE reporting procedures; see Section 8.4 . Discontinue further subject enrollment.

As with all AEs, injection-related signs or symptoms which, in the Investigator’s judgment, are not related to immunologic reactions should be recorded and graded as AEs according to NCI CTCAE v.4.03 criteria in the CRF. Study stopping rules will not apply to a specific event if it is clearly unrelated to INXN-2001 injection (eg, accidental trauma). If an AE associated with injection cannot be definitely shown to be unrelated to INXN-2001, then study stopping rules will apply.

6.2.7 Prophylactic Antipyretic and/or Analgesic Administration

The use of antipyretics and/or analgesics is allowed anytime during study treatment, as indicated, including prophylactic administration.

NOTE: Since fever and flu-like symptoms (eg, fever, headache, chills, dehydration, etc.) are commonly experienced following adenoviral vector administration, it is highly recommended that subjects be treated with prophylactic, antipyretic and/or analgesic medications prior to study drug administration and the first 72hr of each cycle.

Please refer to [Appendix 3](#) for the recommended regimen for the prophylactic administration of antipyretics and/or analgesics.

6.2.8 Disposition of Unused Study Drug

All unused study drug should be destroyed on-site in accordance with applicable site facility and US Occupational Safety and Health Administration procedures, after a full accountability has been documented. Any on-site destruction of unused study drug must be documented and the records maintained in the investigator's study file.

6.3 Concomitant Therapy

Concomitant medication information, including blood products, vitamins, and other supplements, will be collected for the time period beginning 28 days prior to the first dose of study drug through the Post-Treatment Safety Assessment visit.

Permitted:

- Subjects may receive standard treatments, including palliative and supportive care for any underlying illness, with the exception of palliative radiotherapy, which is NOT permitted.
- Antidiarrheal therapy is permitted for study drug-induced diarrhea.
- Antiemetics are permitted for study drug-induced nausea and vomiting. (except those listed [Appendix 2](#))
- Treatment with vitamin/mineral supplements is acceptable provided that they do not interfere with study endpoints, in the opinion of the investigator.

Not Permitted:

- Subjects may not receive medications, foods, or drinks that induce, inhibit, or are substrates of the CYP450 3A4 pathway within 7 days prior to the first dose of study drug through 96 hours after their last dose of INXN-1001. See [Appendix 2](#) for examples.
- Subjects may not receive any other investigational agent or anticancer therapy (chemotherapy, radiotherapy, etc.) while receiving study treatment.

6.4 Evaluation and Assessment Procedures

6.4.1 Schedule of Assessments

A tabular schedule of evaluations and procedures is provided as Schedule of Study Procedures and Assessments following the Protocol Synopsis in [Section 3](#).

6.4.2 Safety Evaluations

6.4.2.1 Demographics and Medical History

Each subject's complete medical history will be documented during screening, including demographic information, relevant medical history, current primary cancer diagnosis, and prior cancer treatments (chemo- and immunotherapies, radiation therapy, surgeries). In addition, concomitant medications, including blood products, vitamins, and other supplements received during the 28 days prior to initiating study treatment will be recorded.

6.4.2.2 Physical Examinations

A complete physical exam will be performed at Screening and at the Post-Treatment Safety Assessment visits. Symptom-directed physical exams will be performed on Day 1 of each cycle.

6.4.2.3 ECOG Performance Status

ECOG performance status will be assessed as provided in [Appendix 1](#).

6.4.2.4 Height and Weight

Height (cm) will be measured during screening. Weight (kg) will be measured at screening, Day 1 of each cycle, and at the Post-Treatment Safety Assessment visit.

6.4.2.5 Vital Signs

Vital signs will include blood pressure, pulse rate, temperature, and respiration rate. Subject's blood pressure is to be monitored closely, with hydration as needed to prevent hypotension for 72 hours after administration of INXN-2001. Blood pressure assessment is required on Days 1, 2, 3 for Cycle 1 and Cycle 2.

6.4.2.6 Adverse Events

Monitoring and recording of AEs and SAEs will be conducted throughout the study. AEs/SAEs that occur following informed consent until the Post-Treatment Safety Assessment must be recorded on the AE CRF; AEs/SAEs that occur prior to informed consent should be added to the medical history CRF.

Definitions, documentation, and reporting of AEs and SAEs are described in [Section 8.0](#).

6.4.2.7 Pregnancy Testing

Females of childbearing potential will have a serum pregnancy test at the screening visit and a urine pregnancy test on the first day of each treatment cycle, prior to administration of INXN-1001.

6.4.2.8 Hematology

Hematology tests include: complete blood count (CBC) and white blood cell (WBC) count, differential WBC count, red blood cell (RBC) count, hematocrit, hemoglobin, RBC indices, reticulocyte count, MCV (mean corpuscular volume) and platelet count. PTT and INR will also be evaluated.

6.4.2.9 Serum Chemistry

Serum chemistry tests include: AST, ALT, LDH, ALP, creatinine, total bilirubin, total protein, albumin, blood urea nitrogen (BUN), glucose, sodium, potassium, chloride, calcium, phosphorus and bicarbonate. The eGFR will be calculated from the serum creatinine at each chemistry time point using the MDRD equation ([Appendix 5](#)); in cases where the MDRD equation may not be suitable, a 24-hour urine creatinine clearance test may be substituted with prior approval of the Medical Monitor.

6.4.2.10 Urinalysis

Urinalysis panel (dipstick) includes: appearance, pH, specific gravity, glucose, protein/albumin, blood, ketones, bilirubin, nitrates, and leukocyte esterase. In addition, a microscopic exam for casts, crystals, and cells may be done if clinically indicated.

6.4.2.11 Electrocardiogram (ECGs)

A standard, single, 12-lead ECG for local safety assessment will be performed at screening, 2.5 to 3 hours after INXN-1001 dosing (and prior to palifosfamide infusion and INXN-2001 injection) on Day 1 of each cycle, and at the Post-Treatment Safety Assessment visit. The ECGs will be used to evaluate the QT/QTc interval.

